11.1 Analysis Sets

11.1.1 Full Analysis Set

The full analysis set (FAS) and safety set are defined in the same way and comprise all subjects who received at least 1 dose of trial treatment. Subjects will be analyzed according to the actual trial treatment received.

11.1.2 Safety Set

See the definition of the FAS.

11.1.3 Per-Protocol Set

Not applicable.

11.1.4 Dose-Determining Analysis Set

The Dose-Determining Set (DDS) consists of all patients from the safety set who either have received between 80% and 125% of the planned dose and have completed the DLT observation period, or have experienced a DLT during cycle 1. This constitutes an evaluable patient for the determination of MTD Statistical Analyses.

11.2 Patient Demographics and Baseline Characteristics

Demographic and other baseline data including disease characteristics will be listed and summarized descriptively for the FAS.

Categorical data will be presented as frequencies and percentages. For continuous data, mean, standard deviation, median, minimum, and maximum will be presented.

Relevant medical histories and current medical history at baseline will be summarized by system organ class and preferred term.

Genmab

11.3 Treatments

The Safety Set will be used for the analyses below. Categorical data will be summarized as frequencies and percentages. For continuous data, mean, standard deviation, median, 25th and 75th percentiles, minimum, and maximum will be presented.

The duration of exposure in months to GEN1029 as well as the dose intensity (computed as the ratio of actual cumulative dose received and actual duration of exposure) will be summarized by means of descriptive statistics using the safety set.

Concomitant medications and significant non-drug therapies prior to and after the start of the IMP will be listed and summarized according to the anatomical therapeutic chemical (ATC) classification system, by dose cohort.

11.4 Analysis of Dose Escalation Part

11.4.1 Primary Objectives

The primary objectives are to:

- Determine the MTD and the recommended Phase 2 dose (RP2D)
- Establish the safety profile of GEN1029.

11.4.1.1 Primary Endpoints

- Number of DLTs during the DLT period (initial 28 days of treatment). See Section 4.3 for how the MTD will be determined.
- Summary tables for adverse events (AEs) will include only AEs that started or worsened during the on-treatment period, the treatment-emergent AEs.

The incidence of treatment-emergent adverse events (new or worsening from baseline) will be summarized by System Organ Class (SOC) and or Preferred Term (PT), severity (CTCAE grade), type of adverse event, and relationship to IMP.

SAEs, non-serious AEs and AEs of special interest (AESI) during the on-treatment period will be tabulated.

All deaths (on-treatment and post-treatment) will be summarized.

All AEs, deaths and SAEs (including those from the pre and post-treatment periods) will be listed and those collected during the pre-treatment and post-treatment period will be flagged.

Further summaries of AEs will be specified in the statistical analysis plan.

11.4.2 Secondary Safety Objectives

11.4.2.1 Clinical Safety Data

Liver toxicity will be described separately as *a priori* this is the most relevant potential safety concern.

11.4.2.2 Laboratory Safety Data

Grading of laboratory values will be assigned programmatically as per the National Cancer Institute's CTCAE version 4.03. The calculation of CTCAE grades will be based on the observed laboratory values only, clinical assessments will not be taken into account.

CTCAE Grade 0 will be assigned for all non-missing values not graded as 1 or higher.

For laboratory tests where grades are not defined by the CTCAE, results will be categorized as low/normal/high based on laboratory normal ranges.

The following summaries will be generated separately for hematology, and biochemistry tests:

• Listing of all laboratory data with values flagged to show the corresponding CTCAE grades, if applicable, and the classifications relative to the laboratory normal ranges.

For laboratory tests where grades are defined by the CTCAE:

- Worst post-baseline CTCAE grade (regardless of the baseline status). Each patient will be counted only once for the worst grade observed post-baseline.
- Shift tables using CTCAE grades to compare baseline to the worst on-treatment value.

For laboratory tests where grades are not defined by the CTCAE:

• Shift tables using the low/normal/high/ (low and high) (or other project-specific) classification to compare baseline to the worst on-treatment value.

In addition to the above mentioned tables and listings, other exploratory analyses, for example figures plotting time course of raw or change in laboratory tests over time or box plots might be specified in the analysis plan.

11.4.2.3 Other Safety Data

ECG

12-lead ECGs including PR, QRS, QT, QTcF, and RR intervals will be obtained for each patient during the trial in accordance with Table 1-2 (dose escalation part) and Table 1-7 (expansion part). ECG data will be read and interpreted centrally.

Categorical analysis of QT/QTc interval data based on the number of patients meeting or exceeding predefined limits in terms of absolute QT/QTc intervals or changes from baseline will be presented. In addition, a listing of these patients will be produced.

Vital signs

Data on vital signs will be tabulated and listed; notable values will be flagged.

11.4.3 Pharmacokinetics

Individual curves of plasma/serum concentration of each component of GEN1029 including information on actual dose, will be presented for all patients. All available data will be shown in these figures. Concentrations below the limit of quantitation will be set to LLOQ/2.

PK parameters (Table 11-1) will be calculated based on non-compartmental methods and will be calculated separately for Cycle 1, Cycle 2 and Cycle 3.

The relation between derived PK parameters and covariates such as actual dose, weight and dose, and selected laboratory parameters will be evaluated graphically.

If deemed applicable compartmental modeling approaches to parameter estimation will be applied.

Further exploratory analyses of PK data may be performed.

Table 11-1 Non-compartmental Pharmacokinetic Parameters

AUC _{0-14days}	The AUC from time zero to day 14 (mass x time x volume-1)
AUC _{inf}	The AUC from time zero to infinity (mass x time x volume-1)
AUC _{last}	The AUC from time zero to last quantifiable measurement
C _{max}	The maximum (peak) observed plasma, blood, serum, or other body fluid drug concentration
	after single dose administration
T _{max}	The time to reach maximum (peak) plasma, blood, serum, or other body fluid drug
	concentration after single dose administration
T _{1/2}	The elimination half-life associated with the terminal slope (λz) of a semi logarithmic
	concentration-time curve
CL	The total body clearance of drug from the plasma

11.4.4 Immunogenicity of GEN1029

As a result of Immunogenicity analysis samples will be scored ADA positive or ADA negative and subsequently reported. From positive ADA samples titer values and neutralizing antibody scores (postivie or negative) will be determined and reported. ADA negative samples with drug on board above the drug tolerance limits of the ADA method will be scored inconclusive due to possible drug intereference. The association between positive/non-positive ADA and PK (predose, AUC, Cmax), major safety signals (CTCAE \geq grade 3) and efficacy information (change in tumor size by CT scan) will be explored.

11.4.5 Secondary Efficacy Objective

The secondary efficacy objective is to further evaluate the anti-tumor activity of GEN1029.

11.4.5.1 Secondary Efficacy Endpoints

11.4.5.1.1 Definition of Response

RECIST criteria (v1.1) will be used to define response. Based on the definition of response (Table 11-2) and the combined evaluation (see Table 1 in Eisenhauer et al., 2009), each patient will be assigned 1 of the following categories at each CT scan visit and as Best Overall Response (BOR):

1) CR

2) PR

3) SD

4) PD or

5) Not Evaluable

BOR is the best response recorded from the start of the treatment until disease progression/recurrence (the smallest measurements recorded since the treatment started will be used as the reference for PD).

	Category	Criteria
Based on	Complete	Disappearance of all target lesions. Any pathological lymph nodes must
target lesions	Response (CR)	have reduction in short axis to < 10 mm.
	Partial Response	\geq 30% decrease in the sum of the LD of target lesions, taking as reference
	(PR)	the baseline sum of LDs.
	Stable Disease	Neither sufficient shrinkage to qualify for PR nor sufficient increase to
	(SD)	qualify for PD, taking as reference the smallest sum of LDs while in trial.
	Progressive	\geq 20% (and \geq 5 mm) increase in the sum of the LDs of target lesions, taking
	Disease (PD)	as reference the smallest sum of the target LDs recorded while in trial or the
		appearance of 1 or more new lesions.
	NE	Not evaluable
Based on non-	CR	Disappearance of all non-target lesions and normalization of tumor marker
target lesions		level. All lymph nodes must be non-pathological in size (< 10 mm short
		axis).
	SD	Persistence of 1 or more non-target lesion(s) or/and maintenance of tumor
		marker level above the normal limits.
	PD	Appearance of 1 or more new lesions and/or unequivocal progression of
		existing non-target lesions.
	NE	Not evaluable

 Table 11-2 Definition of Response (RECIST Criteria v1.1)

LD =Longest Diameter; SD for non-target lesions defined as "Non-CR/Non-PD" by Eisenhauer et al., 2009.

Patients with a global deterioration of health status requiring discontinuation of treatment without objective evidence of PD at that time should be classified as having "symptomatic deterioration". Every effort should be made to document the objective progression even after discontinuation of treatment.

Confirmation

SD: follow-up measurements occurring at least 6 weeks (\pm 7 days) after first treatment must have met the SD criteria at least once.

PR and CR: no formal confirmation response is required. However, a repeat CT-scan may be performed no less than 4 weeks after the criteria for response is met to substantiate/confirm CT response. If the response is still present this will be called confirmed response/confirmed complete response.

Reporting of Objective Response Rate (ORR) results:

Patients in response categories 1 and 2 are considered responders and patients in response categories 4 and 5 are considered as failing to respond to treatment. Patients in response categories 1, 2 and 3 are considered to be in disease control.

Individual patient data listings and summaries of objective response, best overall tumor response and disease control will be presented by dose cohort/indication and total.

The maximal response (maximal reduction in the sum of the LD in the target lesions) in target lesions at any time on trial will be reported using waterfall plots.

11.4.5.1.2 Progression-free Survival

PFS is defined as the time from the date of C1D1 to the date of the first documented progression or death due to any cause. PFS will be assessed via local review according to RECIST 1.1

(Eisenhauer et al., 2009). PFS will be censored in accordance with Table C1 in Appendix C in the FDA Guidance for Industry: Clinical Trial Endpoints for the Approval of Non-small Cell Lung Cancer Drugs and Biologics (FDA 2015).

Progression-free survival will be derived for all patients and presented graphically as well as summarized using survival analysis methods.

The quartile estimates of PFS from the Kaplan Meier product limit algorithm will be presented. The 2-sided 95% confidence interval will be presented as well. The number of events may be small, and thereby limit use of the Kaplan Meier method to provide reliable information. In this case, descriptive statistics (e.g., n, mean, standard deviation, median, minimum and maximum) for PFS will be presented.

11.4.5.1.3 Overall Survival

Overall survival is defined as the number of days from Day 1 in Cycle 1 to death due to any cause. If a patient is not known to have died, then OS will be censored at the latest date the patient was known to be alive (on or before the cut-off date).

Overall survival will only be analyzed for the expansion part using the same techniques and presented in the same manner as PFS.

11.4.5.1.4 Duration of Response

Duration of response (DoR) only applies to patients whose best overall response is complete response (CR) or partial response (PR) and is defined as the number of days from the first documentation of objective tumor response (CR or PR) to the date of first PD or death due to underlying cancer. Subjects continuing without progression or death due to underlying cancer will be censored at the date of their last adequate tumor assessment.

DoR will be summarized in the same way as PFS.

11.4.5.1.5 Time to Response

Time to response (TTR) is defined as the number of days from Day 1 in Cycle 1 to the first documented response of either CR or PR, which must be subsequently confirmed (although date of initial response is used, not date of confirmation). CR and PR are based on tumor response data as per local review and according to RECIST 1.1.

The TTR calculations is restricted to those subjects in the FAS with a confirmed PR or CR. TTR will be listed and summarized by treatment group.

11.4.5.1.6 Tumor Shrinkage

Tumor shrinkage (based on CT-scan evaluations) will be listed and summarized.

11.5 Analysis of Expansion Part

In general, the analysis methodology for the endpoints of the dose expansion part will be the same as the one used for the corresponding endpoints in the dose escalation part, only summarizing by cohort (which is regimen and indication specific).

11.5.1 Primary Objective

The primary objective of the expansion part is to evaluate the ORR by cohort.

11.5.1.1 Primary Endpoint

The primary endpoint for the dose expansion part is the ORR as defined in Section 11.4.5.1. The primary analysis will be based on the confirmed responses. Supportive to this, an analysis using both confirmed and unconfirmed response will be carried out.

11.5.1.2 Statistical Hypothesis, Model and Method of Analysis

If only one regimen is evaluated for an indication there is no formal hypothesis to be tested in the dose expansion part. The ORR will be estimated with exact 2-sided 95% confidence intervals (CIs) for each arm using the Clopper-Pearson method. Other response rates such as BOR and rate of disease control will be reported similarly.

Should there be more than one regimen evaluated for an indication the endpoints will be reported per regimen (and indication) as described above. In addition for each indication tested in multiple regimens, a logistic regression model, adjusted for screening ECOG score and regimen (with two possible levels) will be used to report the comparative efficacy of the evaluated regimens.

The odds ratio in response rates between two initiated regmeins within one indication will be tested at the two-sided 5% Type-I error rate level.

The totality of the data together with the planned comparison will guide the selection of a regimen for further development.

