6.1.2 Treatment Assignment

This is an open-label trial; therefore, blinding of treatment will not be performed. Allocation of patients will be controlled by the CRO.

Escalation Part:

When a potential patient in the dose escalation is identified at a site, the site personnel must contact the CRO for allocation in accordance to Section 4.3. If there is an opening in the currently enrolling cohort, the site will be given approval to start the screening process. If there is no opening in the currently enrolling cohort, the CRO will place the patient on a list of potential patients. If another patient fails the screening process, the CRO will alert the site that has the next patient on the waiting list. If the patient is still eligible, the site will be given approval to start the screening process.

Expansion Part:

In the expansion part, treatment assignment will be done through an electronic system, for example, the interactive response technology (IRT) system. The CRO will oversee the recruitment and notify the sites when cohorts are complete. If only one dose regimen is opened within an indication, eligible patients will be allocated to this. In the situation where more than one dose regimen is available to eligible patients within an indication, patients will be allocated as follows to available regimens:

- If two dose regimens are available within the indication, patients will be randomized in a 1:1 fashion, stratified by ECOG score at screening
- Should one dose regimen within an indication be stopped during the expansion phase, the allocation mechanism will switch to allocation into the one regimen left.

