11.8.3 Statistical Power for Comparing Two Regimens within one Indication

If more than one regimen is evaluated for the same indication in two different cohorts in the expansion part, the response rates in the two cohorts will be compared as described in Section 11.5.1.2). The power (probability of being able to detect a statistically significant difference between two regimens A and B with underlying true response rates θ_A , and θ_B , respectively) for different stages of sample sizes, is presented in Table 11-9. It is noted that the sample sizes at the final analysis may not be equal.

For each scenario, 50,000 trials were simulated, and the logistic regression model (see Section 11.5.1.2) was estimated using SAS PROC GENMOD to test the significance (at the one-sided Type I error rate of 5%) of Regimen *B* being better than Regimen *A*. The power is the percentage of trials were the p-value of the regimen effect was <5% (one-sided). The simulations are constrained on having at least two responders in each cohort at N=20, and at least four responders in each cohort at N=40 and N=60. This reflects the expansion strategy within each cohort and implies that there is some similarity imposed on the realized trials that impacts the following power assessment.

θ_A	$ heta_B$	Power	Power	Power	
		$@N_A = N_B = 20$	$@N_A = N_B = 40$	$@N_A = N_B = 60$	
10%	15%	0%	0%	6%	
10%	20%	2%	5%	24%	
10%	25%	6%	18%	52%	
15%	20%	1%	3%	9%	
15%	25%	4%	11%	26%	
15%	30%	10%	27%	49%	
20%	25%	2%	5%	9%	
20%	30%	6%	15%	23%	
20%	35%	13%	30%	45%	
25%	30%	4%	7%	8%	
25%	35%	8%	15%	22%	

Table 11-9: Power	(Probability to	Detect a S	Significant	Difference	Between tw	wo Regimens)
	· ·		8			

Due to foreseen scenarios and the constraint imposed on the simulations, the probability to conclude that there is a significant improvement with Regimen B over Regimen A is low to moderate. The power ranges from 0% up to 52%, depending on the underlying assumed response rates and the sample sizes. This can also be expressed as that the probability of not being able to detect a difference based on the statistical model lies between 48 and 100%.

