## 3.3 Sample Size Justification

The protocol v9.0 planned to enroll up to approximately 100 subjects shared between the Regimens. As the MTD was found earlier than the highest dose level planned in the protocol and the expansion will not be initiated, only 48 subjects will be recruited.

Of those 48 subjects:

Page 8 of 44

TPL N°: eTPL SA-02-01 Of SOP SA-02.08 TPL Effective Date: 31 Mar 2016

- Two subjects were assigned to the priming regimen:
- One received the priming dose and then continued on a lower dose level. This subject is considered as treated on the 'biweekly regimen'.
- The second subject received the priming dose and continued with a higher dose level, this subject will be analysed as treated in the priming regimen.
- Three subjects were also planned in an Intensified Regimen (8xQ1W/Q2W) all of whom experienced DLTs and, consequently, this dosing regimen was permanently discontinued.

The Intensified Regimen was discontinued per protocol v9.0.

More details on sample size can be found in section 11.8 Sample Size Calculation of the protocol final version 9.0 dated 24 October 2019.

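### The regimen comparison in Protocol 11.5.1.2 is not limited to patients randomised while both regimens were open, so a time trend in response can bias it

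*Protocol*

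**What the plan says.** Protocol 6.1.2 has three allocation rules for the expansion part.

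- Two regimens available in an indication: "patients will be randomized in a 1:1 fashion, stratified by ECOG score at screening".
- One regimen open: "If only one dose regimen is opened within an indication, eligible patients will be allocated to this".
- One of two regimens stopped: "the allocation mechanism will switch to allocation into the one regimen left".

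Protocol 11.5.1.2 then fits a logistic model with screening ECOG score and regimen, which "will be used to report the comparative efficacy of the evaluated regimens". The odds ratio between two regimens that have been initiated is tested at a two-sided 5% level, so a stopped regimen is still compared. The result, with the totality of the data, guides which regimen is developed further. The model has no term for time or enrolment period, and the section does not separate randomised from directly allocated patients.

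On the analysis set, Protocol 11.1.1 states: "Subjects will be analyzed according to the actual trial treatment received". On cohort sizes, Protocol 11.8.3 states: "It is noted that the sample sizes at the final analysis may not be equal".

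SAP section 3 records that the expansion part was not initiated. The SAP covers escalation only and contains no regimen comparison.

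**The concern.** Stratified randomisation protects a comparison only for patients who could have received either regimen. Read as written, the test combines those patients with others who entered when only one regimen was open, and who therefore come from a different calendar period. If response rates change over that time, through new sites, prior therapy or supportive care, the change is attributed to regimen, and ECOG adjustment need not remove it. Analysis by treatment received is a further departure from the randomised groups, although it does not itself create the calendar problem. At stake is the choice of regimen for further development.

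**Working it through.** **1. The plan's own figures.** The first-look stopping probability is (1 − p)^10, because every cohort needs at least 1 responder in 10 (Table 11-7). At the target rates this is 0.85^10 = 0.197, 0.80^10 = 0.107 and 0.75^10 = 0.056. Table 11-8 gives 20%, 11% and 6%. For Table 11-9, a Wald test of the log odds ratio, conditional on the stated minimum responders and without the ECOG term, gives 51.8% against the printed 52% for 10% v 25% at 60 per arm. That match is for a two-sided 5% test, the level in 11.5.1.2. The one-sided 5% level named in 11.8.3 would give 66.8%.

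**2. How often only one regimen continues.** Take two independent cohorts with the same true ORR, at target, and apply the Table 11-7 cut-offs to cumulative responders. Let r be the probability of reaching 60.

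| Indication | Stops at 10, 20, 40 | r | Exactly one reaches 60: 2r(1 − r) |
|---|---|---|---|
| CRC (15%) | 0.197, 0.068, 0.039 | 0.696 | 42% |
| TNBC (20%) | 0.107, 0.029, 0.097 | 0.767 | 36% |
| Other (25%) | 0.056, 0.062, 0.049 | 0.833 | 28% |

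With 1:1 enrolment up to the stop, the surviving regimen then adds 50, 40 or 20 patients without randomisation.

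**3. Bias under drift.** The documents give no drift size, so the changes in ORR below are assumptions. There is no true regimen effect at any time.

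- A enrols 40 alone, then 1:1, final 60 v 60: B − A = p1 − (40·p0 + 20·p1)/60 = (2/3)(p1 − p0). For 15% to 25% this is 6.7 points; for 10% to 25% it is 10 points.
- A stops at n, B continues alone to 60: B − A = ((60 − n)/60)(p1 − p0).

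**4. Rejection rates.** These come from simulation of the two-sided 5% Wald test with no ECOG effect. With 15% throughout and no gates, rejection is 4.2% at 60 v 60.

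A opens first and enrols 40 alone, final 60 v 60. The gated columns apply Table 11-7 to both cohorts and condition on both reaching 60:

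| ORR drift | Ungated | CRC gated | TNBC gated | Other gated |
|---|---|---|---|---|
| 15% to 25% | 13.5% | 9% | 5% | 3% |
| 10% to 25% | 26% | 14% | 7% | 4% |

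The bias in the gated cases is about 4 to 8 points. If ORR falls from 25% to 10%, ungated rejection is 30.9%.

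A stops early and B continues alone to 60 (ungated):

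| A stops at | ORR drift | Bias, B − A (points) | Rejection |
|---|---|---|---|
| 40 | 10% to 20% | 3.3 | 3.4% |
| 40 | 10% to 25% | 5.0 | 5.9% |
| 20 | 10% to 25% | 10.0 | 1.3% |
| 40 | 25% to 10% | −5.0 | 9.1% |
| 20 | 25% to 10% | −10.0 | 17.3% |

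**5. Concurrent patients only.** In the same ungated scenarios rejection is 1.2% to 4.7% at 40 v 40 and 0.2% to 3.6% at 20 v 20. The expected difference is zero.

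**The case against.** The strongest reply is that little is at risk. The expansion part never opened. Protocol section 11 leaves the analysis populations to the SAP, so silence is not a decision to pool. The primary objective is ORR by cohort, and the regimen test is additional and openly low-powered. The largest error rates depend on one regimen opening well before the other within an indication, which no section describes, and on drift that is assumed. They also ignore the futility cut-offs, and with those applied rejection in most indications is at or below 5%. In the documented case, a stop followed by rising ORR, the test is barely affected.

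Most of this stands as a limit on size. It does not remove the gap. The switch after a stop is explicit, 11.5.1.2 has no restriction or period term, and the SAP dropped the comparison without filling the gap. Staggered opening is allowed by the wording of 6.1.2. It is also plausible: the trial began with the Biweekly Regimen (4.2.1), priming may be considered (4.2.2), and the RP2D is set per regimen (4.3). The cut-offs are described as a guideline, and bias in the estimate remains when they are applied.

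A reader might infer from SAP 3.3, where a subject assigned to priming is counted as biweekly after continuing on a lower dose, that early failures leave the priming group. The documents do not support this. The subject was in the non-randomised escalation part and no reason for the lower dose is given. Nor does the protocol say that the regimens are identical in Cycle 1: Table 4-1 defines priming by its Cycle 1 dose.

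**Conclusion.** The point holds as a gap in the Protocol v9.0 design text. Following 11.5.1.2 with 6.1.2 can mix randomised and non-concurrent patients in a test that guides regimen selection, and uneven continuation is likely enough to plan for (28% to 42% of pairs at the target rates, if the cut-offs are followed). The harm is conditional on a real time trend. A shift of several points in the estimate is the more robust consequence. Clear inflation of the test needs staggered opening or falling response, and depends on indication once the futility cut-offs are applied. A reader might conclude that the comparison has a false-positive rate near 26%, or that a reported result is compromised. The first needs an undescribed opening sequence, a large assumed drift and no gating; the second is ruled out because the expansion part was not initiated.

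**What to change.** In 11.5.1.2, state that the regimen comparison within an indication uses patients randomised while both regimens were open in that indication, analysed in the regimen to which they were randomised. An enrolment-period term does essentially the same if periods are defined by which regimens were open. Keep all treated patients, by cohort, for single-arm ORR and for safety, and report the pooled comparison as supportive.

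The cost is a sentence in 11.5.1.2, a flag in the allocation system for randomised versus directly allocated patients, and power when enrolment is not concurrent. By Table 11-9, power for 10% v 25% is 52% at 60 per arm, 18% at 40 and 6% at 20. With only 20 concurrent patients per arm the test is close to uninformative, and the plan should say so rather than recover power from non-randomised patients. No reported analysis changes.
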